We will recruit 40 adult daily, non-menthol smokers to a single 2-hr laboratory study where they will smoke two study-provided [commercially available] cigarettes, each for a 10-min *ad lib* period, and then complete product perception and use measures. Smoking sessions will be video recorded and scored to capture puffing behavior, and carbon monoxide (CO) assessments will be collected before and after smoking to assess changes in acute smoke exposure. We will use a 2 x 2 mixed factorial design to manipulate the study-provided cigarette's packaging (between subject factor: light colored 'Sky' package vs. black NAS package; both industry-made) and filter type (within-subject factor: charcoal filter vs. non-charcoal filter; cigarettes will appear identical despite differences in filter composition). Primary outcomes will be product perceptions (risk perceptions, subjective ratings), use behaviors (puffing behavior and purchase task), and acute toxicant exposure (changes in CO). Our laboratory has extensive experience with administering cigarette products within similar study designs.

METHODS:

1. Study Instruments:

Independent variables:

Cigarette pack type (between-subject condition): We will purchase and repurpose industry-created cigarette packages to randomly assign participants to smoke a study supplied-cigarette in either light colored (i.e., NAS 'Sky') or black (i.e., NAS 'Black') packs.

Cigarette filter type (within-subject condition): We will manipulate cigarette filter type by providing smokers with two cigarettes, one with a charcoal filter and one without a charcoal filter, in counterbalanced order. We will use the NAS 'Orange' and 'Sky' varieties as the non-charcoal and charcoal cigarettes, respectively, as these cigarettes are identical in appearance despite differences in filter composition.

Screening/Descriptive Measures:

Height/weight: Research staff will measure and document participant height and weight utilizing a standard physician's scale.

Medical history: A Medical History Form (led by the research staff) will be completed to review for applicable contraindications previously listed under Key Inclusion/Exclusion Criteria.

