Brand appeal: Participants will be asked to complete a 6-item measure of brand appeal regarding their preferred brand and the two study-supplied cigarettes they smoked during their in-person session. They will be asked to rate the design of the brand of cigarette they currently smoke (or just tried) on the following 6 items: 1) stylish, 2) fashionable, 3) cool, 4) high quality, 5) attractive, and 6) appealing. Responses will be scored using a 7-point likert scale with anchors of “Strongly Agree” and “Strongly Disagree.”

Mouth-level nicotine exposure and compensatory smoking: We will collect and store the filters of the two cigarettes smoked during laboratory sessions for potential future analysis regarding mouth-level nicotine exposure (approximated using the biomarker, solanesol) and compensatory smoking (estimated via digital image analysis).

2. Group Modifications:

There will be no differences in study procedures or questionnaire administration; all participants will complete the same procedures and questionnaires following randomization to filter type and packaging conditions.

3. Method for Assigning Subjects to Groups:

Participants will be randomly assigned to smoke two study-supplied cigarettes from 4 possible combinations of filter type and packaging conditions:

1. Charcoal filter cigarette in light-colored pack (NAS Sky cigarette in NAS Sky pack [i.e., actual product])
2. Charcoal filter cigarette in black-colored pack (NAS Sky cigarette in NAS Black pack)
3. Non-charcoal filter cigarette in light-colored pack (NAS Orange cigarette in NAS Sky pack)
4. Non-charcoal filter cigarette in black-colored pack (NAS Orange cigarette in NAS Black pack)

Each participant will smoke one charcoal filtered and one non-charcoal filtered cigarette, in counterbalanced order (i.e., the within-subject condition), but the participant will be assigned the same package color for both cigarettes (i.e., the between subject condition). Randomization group (filter order and package color) will be determined via internal database and assigned prior to participants' arrival for the session.

4. Administration of Surveys and/or Process:

The following measures will be assessed by staff at the start of the laboratory session:

1. Session onset CO
2. Medical history
3. Height and weight
4. Cigarette brand characteristics

The following measures will be completed by participants prior to trying to smoking any laboratory cigarettes:

1. Demographics
2. EtOH

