Data Processing: The data entry screens will resemble the data collection forms as closely as possible to allow visual referencing during data entry. This data entry module will be configured for single data entry. Participant data will either be entered into REDCap using smart phones, computers, or tablets or be collected by research staff, recorded on study-specific CRFs, and scanned in or entered directly into the appropriate DMS module. Data entry checks will be included in the entry screen designs where appropriate to limit the opportunity for erroneous entries due to mistyping. Such data entry checks would include value range comparisons, valid data type checks, required value checks, and/or skip pattern enforcement. Following telephone eligibility screening, staff will perform subject registration. A randomization module will allow staff to randomize eligible subjects into one of the four randomization groups. At the randomization attempt, the DMS will check the eligibility data to confirm validity. A randomization assignment will then be provided.

Data Quality Assurance: The Data Manager will work closely with the PI to develop a data quality module that will identify data items that may have been collected or entered into the database incorrectly. The module will run automatically to inspect all newly entered or modified data. Staff will review data validation results and take any required corrective action for invalid data. Queries will be recorded and tracked in the data quality module.

Corrections identified for individual data items will be managed by the research staff. All changes made will be recorded in an electronic audit trail and documented using change control procedures.

Monitoring of study progress will be accomplished, in part, through reviewing a set of standard enrollment, tracking, and quality review monitoring reports created by the Data Manager. Data audits will occur after the first participants are enrolled, as well as periodically throughout the recruitment period, to detect data entry errors. Eligible participants will have their source document information compared with the data entered in the database. Any errors will be investigated, resolved, and a plan will be implemented to prevent further errors should concerning patterns emerge.

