6. Complete questionnaires on cigarette characteristics (Cigarette Brand Form_*Staff should physically view preferred brand of cigarette pack), demographics, ETOH history, smoking history, nicotine dependence (FTND), craving (QSU), withdrawal (WSC), quitting motivation (contemplation ladder), risk perceptions (Risk Beliefs & Perceived Health Risks), Purchase Task, and Brand Appeal.

7. Smoke two study provided cigarettes interspersed by 45 minutes in the smoking lab while video-recorded.
 - a. Participants will complete a harm perceptions questionnaire before smoking each cigarette.
 - b. CO will be assessed before and after each cigarette smoked in the lab.
 - c. Subjective Cigarette Ratings (VAS), Risk Beliefs, Perceived Health Risks, Purchase Task, Attitudes/Intentions, and Brand Appeal will be assessed after each cigarette smoked in the lab.
 - d. Used cigarette filters will be collected and stored for potential future analysis.
8. Complete the Final Cigarette Rating Scale and NAS & Charcoal Knowledge questionnaires.
9. Receive Debrief Script and study payment
 - a. Participants will be debriefed as to the full purpose of the study and compensated for their time.

2. Data Collection:

As detailed in the Data Management section, we will use both paper and electronic forms (via REDCap) surveys to collect participant data.

3. Genetic Testing:

Not applicable.

4. Use of Deception:

To avoid biasing participants' perceptions and use of the study cigarettes, we will not explicitly state in any materials (e.g., flyers, consent form) that the study's purpose is to evaluate the effects of cigarette packaging and filter composition. Instead, individuals will be told that we are recruiting volunteers to "evaluate different commercially available cigarettes."

Deception is acceptable in the present study because the study is minimal risk, and participants will be debriefed within the same session that the deception occurs.

Deception is necessary and scientifically valid in this instance because we are interested in how certain design and marketing features used to promote cigarettes implicitly affect smokers' perceptions and use of those products; if we were to inform participants that we were specifically interested in their reactions to the filter and packaging, they may respond in ways that they otherwise would not.

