To inform subjects prospectively of the use of deception/incomplete disclosure, we have included the following suggested consent language on our consent document (see Informed Consent document): "In some research studies, the investigators cannot tell you exactly what the study is about before you participate in the study. We will describe the tasks in the study in a general way, but we can't explain the real purpose of the study until after you complete these tasks. When you are done, we will explain why we are doing this study, what we are looking at, and any other information you should know about this study. You will also be able to ask any questions you might have about the study's purpose and the tasks you did. Though we may not be able to explain the real purposes of the study until after you complete the tasks, there are no additional risks to those that have been described in this consent form."

Upon completing the full survey, participants will be debriefed of the true study purpose. They will be told that we were specifically interested in understanding the effects of cigarette packaging and filter type on their perceptions and use of the product, and that we were initially vague about our procedures to avoiding biasing their responses toward the study manipulations.

5. Statistical Analysis:

Analytic plan. Main and interaction effects of filter and pack type will be analyzed using univariate analysis of variance (ANOVA) models in SPSS IBM Statistics v26. Primary outcomes are continuous, and based on previous work^{17,21,22} are expected to meet normality assumptions. Analyses will first include only main and interaction effects, then will include as covariates any baseline variables demonstrating a bivariate association of $p < 0.25$ with a given outcome measure.

Power analysis and sample size. A priori power analyses were conducted for primary aims using G*Power v3.1.9.2. These analyses determined that a target sample size of 40 will be adequate to detect a significant small-to-medium effect (partial $\eta^2 = .05$, $\alpha = 0.05$, within-subject correlation = 0.5) of the 2 x 2 between-within subject interaction on a univariate outcome with 80% power.

RISK/BENEFIT ASSESSMENT:

1. Risks:

The potential risks to participants, and their likelihood and seriousness, are minimal and described below. Participants can choose, as an alternative, to not enroll in this study.

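### Filter order is randomised but the analysis model has no cigarette-position term; adding position and position × pack protects the filter and interaction tests at little cost

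*Combined protocol and SAP*

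**What the plan says.** **Design.** METHODS section 1 (Study Instruments, independent variables) makes filter type a within-subject factor by "providing smokers with two cigarettes, one with a charcoal filter and one without a charcoal filter, in counterbalanced order". METHODS section 3 (Method for Assigning Subjects to Groups) states "Randomization group (filter order and package color) will be determined via internal database and assigned prior to" the visit, and adds that "the participant will be assigned the same package color for both cigarettes". METHODS section 5 (Data Management, Data Processing) confirms four groups: "A randomization module will allow staff to randomize eligible subjects into one of the four randomization groups". STUDY PROCEDURES section 1, item 7, sets the timing: "Smoke two study provided cigarettes interspersed by 45 minutes in the smoking lab while video-recorded".

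**Analysis.** STUDY PROCEDURES section 5 (Statistical Analysis) specifies ANOVA models for filter, pack and their interaction. "Analyses will first include only main and interaction effects"; the models "then will include as covariates any baseline variables demonstrating a bivariate association" at p < 0.25 with the outcome concerned. Neither order nor cigarette position is named in either step. The power statement rests on partial η² = 0.05, α = 0.05, "within-subject correlation = 0.5" and 40 participants, for 80% power on the 2 × 2 interaction.

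**The concern.** Aim 1 (filter) and Aim 3 (filter × pack) both rest on the charcoal minus non-charcoal difference within a person. A change from first to second cigarette, for example through satiation or familiarity with the questionnaires, enters that difference with one sign when charcoal comes first and the opposite sign when it comes second. If position is not in the model, this spread counts as error.

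The covariate step does not reliably repair it. Order is an assigned factor and is not listed as a baseline variable. Even if it were screened, its entry would depend on the data, outcome by outcome. A position shift also cancels in a person's mean over the two cigarettes, so a bivariate screen on order could miss it.

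What is at stake is mainly precision. If completers' orders happen to be unequal, the filter or interaction estimate is also biased for that particular allocation. The pack main effect is tested between persons and is not affected. CO boost is less exposed to a drift in CO level, because it is already a change from each cigarette's own pre-smoking reading. Ratings, risk beliefs, puffing and the purchase task have no such protection.

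**Working it through.** **Inputs from the plan:** N = 40 (20 per pack), partial η² = 0.05, α = 0.05, within-subject correlation ρ = 0.5, two measurements per person. **Assumed, because the documents give no figure:** outcome SD 1; ρ net of position unless stated otherwise; shift p from 0 to 1.0 SD.

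**Step 1: reproduce the stated 80%.** Under the G*Power default convention, f² = 0.05/0.95 = 0.0526 (f = 0.229) and λ = f² × N × 2/(1 − ρ) = 0.0526 × 40 × 2/0.5 = 8.42. With 1 and 38 df the critical F is 4.098 and power is 0.807. The plan's figure is reproduced.

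**Step 2: cost of the extra terms with balanced order.** Error df go from 38 to 36, the critical F becomes 4.113, λ is unchanged, and power is 0.806.

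**Step 3: effect of leaving position out.** The within-person difference has variance 2(1 − ρ) = 1. The planned interaction is a difference of differences δ with δ²/(1/20 + 1/20) = 8.42, so δ = 0.918. With balanced order, a shift p adds p² to the variance left in the error; at p = 0.5 the variance goes from 1 to 1.25. Simulated results, common shift in both packs:

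| Shift (SD) | Interaction power, no term | With position + position × pack | Filter type I error, no term |
|---|---|---|---|
| 0 | 0.81 | 0.81 | 0.05 |
| 0.25 | 0.79 | 0.81 | 0.043 |
| 0.5 | 0.73 | 0.81 | 0.028 |
| 0.75 | 0.64 | 0.81 | 0.014 |
| 1.0 | 0.51 | 0.81 | 0.006 |

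If the shift is 0 SD in one pack and 1 SD in the other, power is 0.66 with no term, 0.73 with position alone and 0.81 with both terms.

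**Step 4: unequal order among completers.** With a 13:7 split in both packs and a common 0.5 SD shift, the filter estimate is off by 0.5 × (13 − 7)/20 = 0.15 SD. Type I error is about 0.106 without the terms and 0.05 with them. With shifts of 0 and 1 SD and the same split, the interaction is off by 1 × 6/20 = 0.30 SD. Type I error is then 0.074 with no term, 0.105 with position alone and 0.05 with both.

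The terms cost more when order is unequal, because λ is multiplied by 4n₁n₂/20². At 11:9, 12:8 and 13:7 in both packs the factor is 0.99, 0.96 and 0.91, and power is 0.802, 0.790 and 0.768.

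**Step 5: average over allocations, common shift.** Interaction power without / with both terms:

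| Shift (SD) | Simple randomisation to four groups | 60 allocated equally, 40 complete at random |
|---|---|---|
| 0 | 0.796 / 0.771 | 0.805 / 0.796 |
| 0.25 | 0.770 / 0.771 | 0.783 / 0.796 |
| 0.5 | 0.707 / 0.773 | 0.722 / 0.796 |
| 0.75 | 0.608 / 0.773 | 0.626 / 0.795 |
| 1.0 | 0.503 / 0.771 | 0.498 / 0.795 |

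Filter type I error without the terms, at 0.5, 0.75 and 1.0 SD, averages 0.051, 0.051 and 0.050 under simple randomisation, and 0.036, 0.025 and 0.017 under equal allocation. The stated test is therefore not materially anti-conservative on average.

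**Step 6: the other reading of ρ.** If 0.5 already contains position variance, the residual variance is 1 − p². Balanced power without / with the terms is then 0.81/0.83, 0.84/0.90 and 0.89/0.99 at 0.25, 0.5 and 0.75 SD.

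**The case against.** The strongest reply is that nothing may need protecting. No position effect is documented for any outcome. A correlation pooled over counterbalanced orders would naturally include position variance, in which case power never falls below plan. This stands as a limit on the claim: the losses in Step 3 are conditional on one reading of ρ. Under the other reading the terms still add power.

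A second reply is that position × pack is the weaker term. For a common shift of 0.5 SD, position alone averages 0.786 against 0.772 with both terms under simple randomisation, and 0.800 against 0.795 under equal allocation. That is correct, and the extra term costs about one point. It is, however, the only term that recovers a pack-specific shift, and it follows the four groups as randomised.

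Third, the 13:7 example is rare. A split at least that uneven, in the same direction in both packs, has probability 2 × 0.1316² = 3.5% under simple randomisation and about 0.04% under equal allocation of 60. It shows the mechanism, not the expected case. An overall split of 24:16 or worse is more likely: 26.8% and 5.4% respectively.

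Fourth, all power figures use the G*Power default effect-size convention. If 0.05 were the within-stratum partial η² that SPSS reports, baseline power would be about 0.28 to 0.29, and a 0.25 SD shift would matter little in absolute terms. This too is correct, and is a separate question about the sample-size statement.

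Finally, this is a pilot. That argues against treating the point as critical, not against a one-sentence change.

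**Conclusion.** The point holds. The plan randomises order and then omits it from the model for the two tests that depend on it. With balanced order and ρ = 0.5 net of position, a 0.5 SD shift costs about 7 points of interaction power (0.81 to 0.73), and a 1.0 SD shift costs 30 (0.81 to 0.51). The terms restore the planned level. With no shift they cost 0.1 point in a balanced design, and 0.9 to 2.5 points averaged over allocations. Under simple randomisation the two models break even at about 0.25 SD; above that the terms gain.

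The omission brings no bias under balanced order and no average inflation of type I error, so the gain is mainly precision, plus protection against an unlucky split. The shift sizes are assumptions throughout. This is a recommended change, not one on which the validity of the study turns.

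**What to change.** In STUDY PROCEDURES section 5, replace the model statement with wording such as:

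> Each outcome will be analysed with a repeated-measures ANOVA or a linear mixed model (participant random) with fixed effects for filter, pack, filter × pack, cigarette position (first or second) and position × pack.

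Name one of the two methods, and say that the position terms are in the first step and stay in the covariate-adjusted step, so that their entry never depends on the p < 0.25 screen. In SPSS GLM Repeated Measures, enter order group as a second between-subject factor crossed with pack; this also takes the pack test from 38 to 36 df, a trivial loss. In SPSS MIXED, enter position and position × pack directly.

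Add one limitation: these terms remove a first-to-second shift, whether common or pack-specific, but not unequal carryover between filter types. Such carryover biases the filter effect by half the carryover difference; for example, 0.5 SD after charcoal and none after non-charcoal gives 0.25 SD.

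The cost is one sentence, no new data and two error df, plus the modest loss of power already shown when completers' orders are unequal or there is no shift.
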